The data collected here will be used to test and further develop respiratory 'signatures' to accurately detect SIRD and differentiate from patterns that occur following substance use but do not result in an overdose. Wearing the device will not alter the services participants receive at the supported accommodation.

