3 OBJECTIVES AND OUTCOME MEASURES/ENDPOINTS

To establish that the DC Mobile can be used in a supported accommodation environment to record and retrospectively detect changes in chest movement consistent with respiratory patterns of an accidental drug overdose.

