7.4 Study assessments

Participants will answer questions to determine their demographics such as age, BMI and gender at birth. If required, participant will be weighed and measured to calculate their BMI. Participants will be asked if they have any existing respiratory medical conditions. After wearing the biosensor, participants will complete a short satisfaction survey on their experience of PneumoWave DC. Participants should complete this at least once. Participants who stay at the site for a longer period may complete more than one to show fluctuating levels of acceptance. Participants will be asked to complete a drug use diary and an AIR tool to describe their drug use. Drug use and care is discussed with participants so these can be completed in the presence of and with support of, site staff.

During welfare checks, site staff will record any evidence of drug use in the pCRF. If a participant requires intervention due to a potential overdose event, site staff will record this in the pCRF, along with the level of intervention required, if the participant is unresponsive. Where possible the biosensor will be left on the participant during the intervention, and removed once the participant has sufficiently recovered or prior to leaving the facility (i.e. transfer to a medical facility).

A subsection of participants will be asked to partake in semi-structured interviews, lasting no longer than 60 minutes, to describe their experience wearing the device.

A further subsection of participants, including those who may have had an interview, will be asked to take part in focus groups to discuss the PneumoWave DC Mobile and the prototype for the Alert system and the perceived benefits or downsides it may have.

Staff from across all participating supported accommodation will be invited to take part in a semi-structured interview and/or a focus group to discuss their views on, perceived benefits of or barrier to use of the biosensor and DC Mobile system.

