10.3.2 Primary outcome analysis

- Biosensor data analysed to determine whether or not an alarm would have been raised (and possibly the timing of the alarm)
- Staff measured outcomes reviewed to categorise whether there was cause for concern about the participant
- Above measures compared to determine either True Positive / False Positive / True Negative / True Positive events
- Sensitivity and Specificity are calculated for the complete data set (ideally with error bars calculated by an appropriate statistical method)

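### The primary analysis scores the algorithm against an undefined staff-concern category with optional alarm timing, so its sensitivity and specificity need not measure accuracy for overdose or SIRD

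*Protocol*

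**What the plan says.** Section 10.3.2 of the protocol builds a two-by-two comparison.

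- **Index test:** whether the retrospective algorithm would have raised an alarm, "and possibly the timing of the alarm".
- **Reference:** "Staff measured outcomes reviewed to categorise whether there was cause for concern about the participant".
- **Comparison:** "Above measures compared to determine either True Positive / False Positive / True Negative / True Positive events". The list prints true positive twice and has no false negative, which looks like a slip. No unit of analysis or matching window is given.
- **Output:** "Sensitivity and Specificity are calculated for the complete data set".

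The target is named elsewhere. Section 3 speaks of chest-movement changes "consistent with respiratory patterns of an accidental drug overdose". Section 2 wants signatures that detect SIRD and "differentiate from patterns that occur following substance use but do not result in an overdose", and justifies the setting as one where overdose can be confirmed or ruled out from outside the device.

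Section 7.4 has staff record two different things in the pCRF: evidence of drug use seen at welfare checks, and intervention for a potential overdose, "along with the level of intervention required, if the participant is unresponsive". Section 11.1 lists potential SIRD events and their outcomes among the CRF items, and section 3.1 counts overdose among the staff-measured outcomes.

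**The concern.** Sensitivity and specificity belong to a test and a target condition together. Here the target is overdose or SIRD, but the truth column is a broader word with no criterion attached. A resident who is heavily intoxicated but not in overdose could reasonably be judged a concern. That is the very class the rationale wants told apart from overdose. If it is counted as reference-positive, an algorithm that fires only on overdose looks insensitive, and one that fires on sedation is rewarded.

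Optional timing is a second, separate problem. Without a rule linking alarm time to event time, an alarm hours away from the event can be scored as having detected it. The longer the unit of analysis, the more often this happens by chance.

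The study's data are meant to test and refine the algorithm, so a misread accuracy figure would carry into its further development.

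**Working it through.** The protocol gives no accuracy figure, event rate or sample size calculation (section 10.1), so there is no figure to reproduce. The rates below are assumptions, used only to show how each feature acts.

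**1. Reference broader than the target.** Let p be the prevalence of SIRD per unit, s the chance that staff flag a SIRD unit, and q the chance that they flag a unit without SIRD. Assume that alarms and staff flags are independent given SIRD status. Then

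apparent sensitivity = [p·s·Se + (1−p)·q·(1−Sp)] / [p·s + (1−p)·q].

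Take true Se = 0.90, Sp = 0.95 and s = 1. For p = 2% and q = 5%: (0.02×0.90 + 0.98×0.05×0.05) / (0.02 + 0.98×0.05) = 0.02045/0.069 = 0.30. The full grid:

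| p | q = 2% | q = 5% | q = 10% |
|---|---|---|---|
| 1% | 0.34 | 0.19 | 0.13 |
| 2% | 0.48 | 0.30 | 0.19 |
| 5% | 0.67 | 0.49 | 0.34 |

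Apparent specificity stays at 0.95. With q = 0 the formula returns 0.90. The result is a weighted mean of the alarm rates in flagged units with and without SIRD. It therefore falls whenever alarms are less frequent in the units without SIRD, and falls less if the algorithm also responds to intoxication.

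**2. Untimed matching within a night.** Suppose alarms are random, with mean λ per 8-hour night, and unrelated to any event. If any alarm that night counts, sensitivity is 1−exp(−λ) and specificity is exp(−λ). With a 1-hour window the chance of a credited alarm is 1−exp(−λ/8).

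| λ per night | Sensitivity, untimed | Specificity, untimed | Chance of a match in 1 hour |
|---|---|---|---|
| 1 | 63% | 37% | 12% |
| 0.2 | 18% | 82% | 2.5% |

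Untimed sensitivity and specificity sum to 1, as they must for an uninformative test.

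**3. Longer units.** The study summary allows one night to 4 weeks, extendable by 4 weeks. If the unit were a 28-night stay and random alarms fell on 5% of nights, chance sensitivity would be 1−0.95^28 = 0.76, with specificity 0.24. For a one-night unit the pair is 0.05 and 0.95.

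**4. A partly informative algorithm.** If a fraction d of events draws a timely alarm and random alarms are added, untimed sensitivity is d + (1−d)(1−exp(−λ)). The second term is chance credit, and a time window removes most of it.

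**5. Together.** The broad reference pulls apparent sensitivity down in this model, and untimed matching pushes it up. The protocol gives nothing from which to work out the net effect.

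**The case against.** The strongest reply is that much of this belongs in the SAP, which section 10.3 promises before data lock and which is not at hand. It could define the concern category, the unit and the window. The staff outcomes already include overdose, so the category might in practice be built from the overdose records. This is also a feasibility study whose tabulated primary objective is to capture chest motion data. All of that stands, and it limits the point to undefined breadth and optional timing. It does not remove the point: the protocol itself names a reference that can be wider than its own target and marks timing as optional. A SAP that used recorded overdose as the reference would be narrowing what section 10.3.2 says.

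A reader might infer four stronger things that the document does not support.

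- **That the category is assigned with the alarm result in view.** The protocol is silent. Staff make their records without any alert (section 2.1), and the algorithms are applied retrospectively, outside DC Mobile (section 8.1). Only the later review step is open.
- **That a random algorithm would pass as good.** Its 63% sensitivity comes with 37% specificity, and section 10.3.2 asks for both, so the pair would expose it.
- **That the study cannot address discrimination at all.** Drug-use evidence and overdose interventions are recorded separately, so the data needed are being collected.
- **That only events needing intervention should count as positive.** The target includes SIRD, so correct alarms on SIRD that resolved without intervention would then be scored as false positives.

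**Conclusion.** The concern holds in this form: followed as written, section 10.3.2 yields a sensitivity and specificity that need not refer to overdose or SIRD, and it permits alarms unrelated to an event to count as true positives. The first part rests on the undefined category set against sections 2 and 3, the second on the optional timing and the absence of a matching rule.

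The size of the bias is unknown. The 0.13 to 0.67 range and the random-alarm pairs are illustrations on assumed rates, and the two effects act in opposite directions on sensitivity. The change is worth making because it is cheap and uses records already planned. The document does not show that the result would be wrong by any particular amount.

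**What to change.** Amend section 10.3.2, and carry the same wording into the SAP:

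1. Define reference-positive as a staff-recorded potential overdose or SIRD event (sections 7.4 and 11.1). Report events requiring intervention as a subset, and keep the staff-concern category as a sensitivity analysis.
2. Report specificity separately for periods with drug use but no recorded event and for periods with no recorded drug use.
3. Make alarm timing mandatory, state the unit of analysis, and count a true positive only when the alarm falls within a pre-set window around the recorded event or check time.
4. State that the category is assigned from the pCRF without sight of the algorithm output. Section 10.4 has biosensor data reconciled with staff records, so also state that assignment comes before that step.
5. Correct the list of outcomes so that it includes false negatives.

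**Cost.** Wording in the protocol and SAP, and a time entry on the pCRF if it lacks one (the form is not shown). The narrower reference gives fewer positive events and a wider interval for sensitivity. SIRD that staff did not record would be misclassified as negative, so a correct alarm on it would count as a false positive. The report should state that limit.

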2 RATIONALE

Recently, technological developments in wireless 'wearable' devices have enabled real-world, real-time measurement of physiological functioning. Remote measurement of respiratory, cardiovascular, and motor function has the potential to detect opioid overdose automatically and reliably (Goldfine, 2020). However, currently available wearable devices have no ability to detect respiratory depression and have limited utility for use as regulated medical devices. Existing chest-worn vital sign sensors are not practical or economically viable for individual use in the community. In addition, little research into the efficacy of remote overdose detection has been conducted. A chest sensor that reliably detects the overdose breathing signature could alert the emergency services and save lives, when fully developed and used in the community. Qualitative study results indicate that this technology would be positively accepted by people who use drugs (PWUD) (Tas, 2023).

The PneumoWave DC Mobile chest biosensor is a small cylindrical device (40mm diameter 14mm height) that sticks onto the chest using a small plastic patch (an ECG sticker) and measures chest motion. PneumoWave are developing an Alert algorithm (that will be incorporated in the DC Mobile system) that will detect reduced chest movement linked to Substance Induced Respiratory Depression (SIRD). To gather device utility and wearability feedback, and refine the Alert analysis algorithm a study is required on patients at high risk of SIRD to capture chest motion during times when possible consumption events might be occurring, where absence or presence of overdose can be externally verified.

Over a six to eight month period, we aim to capture approximately 50 participants known to use opiate drugs, including opioid injection, wearing the device for multiple nights in supported accommodation centres in the UK. Participants will consent to wear the chest-worn device during their residence at the supported accommodation. Chest motion data will be collected on the device securely and pseudo-anonymously (i.e. study ID will be used; no personally identifiable information will be stored alongside chest motion data) and streamed to a secure cloud.

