2.1 Assessment and management of risk

There is zero to minimal risk to participants from the biosensor itself. It may be mildly uncomfortable to wear initially but participants should soon become used to it. Several Clinical Research projects have been conducted with the technology (eg. *RESCU: RESpiratory monitoring reduCing drUg harm*, IRAS 301153) with over 150 participants and 15,000 hours of wear. No adverse events related to the biosensor have been reported.

There is no risk of personal data being revealed via the DC Mobile software. All chest movement data is anonymous.

Participants are people who actively use drugs and may be at risk of accidental overdose. Supported accommodation sites involved in the study have trained staff to administer naloxone, to reverse the effects of an opioid overdose or to administer first aid. Participants will be informed that the device will not issue an alert in the event of a potential overdose. Supported accommodation staff perform regular wellness checks on residents who show signs of drug use throughout the evening. Staff will continue to perform these checks on study participants, so there is no change to the risk of accidental overdose.

Sites provide advice and additional services to help residents stop using opiates and other drugs. Participants will not be disincentivised from using these services.

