4 STUDY DESIGN

This is an observational study. It will not incorporate any randomisation or intervention. Participants' health care and the management of any potential SIRD event will not be altered by the procedures of the protocol.

People who use drugs often live in supported accommodation, either for short periods or over a period of years. Many may continue to use drugs while on these premises. To stay at these premises people must be registered as a resident. Short term residents must register before they take up accommodation. Potential participants will be opportunistically recruited by staff working in these premises who are trained to fully explain the study and take informed consent. Drug use is discussed with residents for their own safety. Accommodation staff engage regularly with this population and will be able to identify those who may be eligible. This lowers the risk of them approaching people who do not use drugs and potentially causing unintentional offence or stereotyping. Some supported accommodations will provide injecting equipment on request. This would identify a potentially eligible participant. Consented participants will be recorded on an enrolment log at each participating site. The enrolment log is for administration purposes only and will only be available to site personnel.

The study will utilise the PneumoWave DC Mobile biosensor and data collection platform which includes a wearable biosensor that attaches to the press-stud on a supplied and approved ECG electrode. The biosensor can be placed in a number of locations on the chest and diaphragm area, and automatically connects to a Data Hub via Bluetooth (Fig. 1). The position of the biosensor should be changed weekly. In this study the Hub will be a mobile computing platform (Application running on a tablet). The tablet will be held in a secure location, remaining in range of connection for the PneumoWave DC Mobile biosensor. The tablet has no functionality beyond running the monitoring app. Participants will be informed of this and the tablet's location in their residence. Please see further details in the Study Assessments section (section 7.4).

Figure 1:

Participants receive the device to wear and a tablet with the DC Mobile app downloaded to record data while they are in their accommodation. The wearable device battery will be changed 1-2 times per week.

Long term residents: monitored for 4 weeks or longer up to 8 months

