Supported accommodation staff will check in weekly with participants to ensure the device is being worn, is working and the associated tablet is also present and in a working condition. Participants will receive £25 per week if these conditions are met (further detailed in Payment section). This will encourage participants to look after the device and tablet as only a limited number of each will be available at each site. Site staff will check in on participants overnight to check the device is being

worn and the app is running and note any potential drug use. Participants will be asked to wear the device for 4 weeks initially, with an option to extend the period, if agreed. This continues until the participant declines to be part of the study any longer or the study end point is reached, whichever is first.

Short term residents: monitored overnight

Participants will receive the biosensor and tablet to use overnight and return in the morning. They will receive £5 for returning both the biosensor and device in the morning. Up to a maximum of £25. If they remain a resident, they will recollect the biosensor and tablet for all nights that they are resident. This continues until the participant declines to be part of the study any longer or the study end point is reached, whichever is first. Site staff will be trained to ask for ongoing consent if there are three or more nights where the participant has not been resident at the supported accommodation, following initial informed consent. Site staff will check in on participants to check the device is being worn and the app is running and note any potential drug use.

Applicable to all residents/participants:

It is not expected that participants will always be at a participating site. When leaving the site, the biosensor should be left behind along with the tablet. The biosensor can continue to collect chest movement data while out of range of the tablet for 10-12 hours, once back in range, data will automatically be sent to the tablet. A light on the biosensor will flash red for the duration of time it is out of range.

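### Specificity is planned only over the complete data set, so the comparator named in the rationale, substance use without overdose, is diluted by monitored time without use

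*Protocol*

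**What the plan says.** Section 2 (Rationale) sets the task. The signatures must detect SIRD and "differentiate from patterns that occur following substance use but do not result in an overdose". The study is needed to "capture chest motion during times when possible consumption events might be occurring, where absence or presence of overdose can be externally verified".

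Section 10.3.2 (Primary outcome analysis) determines for the sensor data whether an alarm would have been raised. The reference side is "Staff measured outcomes reviewed to categorise whether there was cause for concern about the participant". The two are cross-classified, and then "Sensitivity and Specificity are calculated for the complete data set". Drug use enters neither the classification nor the summary.

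Recording is not tied to consumption. Under section 4, long-term residents are "monitored for 4 weeks or longer up to 8 months", and short-term residents return the kit each morning but "they will recollect the biosensor and tablet for all nights that they are resident".

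Two markers of use are collected. Under section 7.4 staff note evidence of use at welfare checks. Under section 11.1 there is a drug use diary, completed at the participant's discretion.

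**The concern.** Specificity depends on what makes up the negative set. A breathing record from a period without drugs is likely to be an easier negative than one from a sedated participant who comes to no harm. Section 2 itself treats the second kind as the pattern that has to be told apart from SIRD. When both kinds are pooled, the result moves with the amount of no-use time recorded as well as with the algorithm's performance.

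An algorithm that alarms often during ordinary opioid sedation could therefore show a reassuring specificity. The results are meant to test and refine the Alert algorithm, so such a figure could misdirect that work. No other analysis in the protocol supplies the contrast: section 10.3.3 describes only qualitative methods, and section 10.4 only excludes data that do not reconcile.

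**Working it through.** **No figure to reproduce.** Section 10.1 states that the recruitment target rests on no sample size calculation, and the protocol gives no target specificity. The check is therefore the identity for a pooled proportion.

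**Inputs**
- *f*: the share of negative units that follow use without overdose. Not given; varied below.
- Sp_use and Sp_no: specificity in use-without-overdose units and in no-use units. Not given; assumed.

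**Formulas**
- Pooled specificity = *f* × Sp_use + (1 − *f*) × Sp_no
- Overstatement relative to Sp_use = (1 − *f*) × (Sp_no − Sp_use)

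The overstatement is positive whenever Sp_no exceeds Sp_use, and zero if the two are equal or if every negative follows use.

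**Example**, Sp_use = 80% and Sp_no = 98%:
- *f* = 90%: 0.9 × 0.80 + 0.1 × 0.98 = 0.818, overstatement 1.8 points
- *f* = 10%: 0.1 × 0.80 + 0.9 × 0.98 = 0.962, overstatement 16.2 points

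**Range**: pooled specificity, with the overstatement in points in brackets

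| Assumed Sp_use / Sp_no | *f* = 90% | *f* = 60% | *f* = 30% | *f* = 10% |
|---|---|---|---|---|
| 90% / 99% | 90.9% (0.9) | 93.6% (3.6) | 96.3% (6.3) | 98.1% (8.1) |
| 80% / 98% | 81.8% (1.8) | 87.2% (7.2) | 92.6% (12.6) | 96.2% (16.2) |
| 70% / 99% | 72.9% (2.9) | 81.6% (11.6) | 90.3% (20.3) | 96.1% (26.1) |

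**Effect of the undefined unit.** Section 10.3.2 speaks of events without saying whether an event is a night, an hour or a staff check. Suppose a participant has 2 hours of post-use time every night, and hold the specificities at 80% and 98% for simplicity, although in practice they would also change with the unit.
- Whole night as unit: *f* = 100%, pooled 80.0%, no overstatement.
- Hourly windows in an 8-hour night: *f* = 2/8 = 25%, pooled 0.25 × 0.80 + 0.75 × 0.98 = 93.5%, overstatement 13.5 points.
- Hourly windows over 24 hours: *f* = 2/24 = 8.3%, pooled 0.083 × 0.80 + 0.917 × 0.98 = 96.5%, overstatement 16.5 points.

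The same behaviour and the same assumed performance give anything from no overstatement to about 16 points, depending on a unit that the protocol does not state.

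**The case against.** **Pooled specificity is a legitimate measure.** Section 3 aims to show that the system can be used in supported accommodation to record and retrospectively detect overdose-like changes. False alarms over all wear time matter for that aim. This stands, and the pooled figure should be kept.

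**The negatives may be mostly use periods.** Current opiate use is an inclusion criterion (section 6.1), and section 2.1 describes wellness checks on residents who show signs of drug use. If events are tied to those checks, or if the unit is a night and use is near-nightly, dilution is small. Section 4 also has overnight checks that the device is worn, so this reading is possible but not assured. It limits the size of the point without removing it.

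**Stronger readings that the documents do not support.**
- A reader might infer that no-use time replaces the stated comparator. It does not: the complete data set also contains use-without-overdose time.
- A reader might infer that the drug-use data lie idle. Section 3.1 links potential SIRD events to drug-use behaviour through the diary, the AIR tool and the CRF, and section 10.4 reconciles sensor data with staff and patient reports. Neither step, however, gives a specificity by use.
- A reader might infer from "Sites provide advice and additional services to help residents stop using opiates and other drugs" that long-term residents will contribute many drug-free nights. The protocol does not say how many will reduce or stop.

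**Recorded use is an imperfect marker.** The diary is optional and staff note only what they see, so recorded use may over-represent visible sedation. This stands. It is the reason to report the recorded-use figure beside the pooled one instead of replacing it.

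**The SAP could add the split.** It could, and section 10.3 says a SAP will be finalised before data lock. But the protocol itself fixes the data set for this analysis, and as written that choice does not answer the question in section 2.

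**Conclusion.** The point holds as one of dilution. Section 10.3.2 summarises specificity only over the complete data set, while section 2 asks about a narrower contrast that no stated analysis isolates. The direction is upward on one condition, that specificity is worse after use than without use. That is plausible, but the protocol gives no data to confirm it.

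The size cannot be determined. With assumed specificities of 80% and 98% it is about 2 points when 90% of negatives follow use and about 16 points when 10% do. Other assumed pairs in the table run from about 1 to about 26 points. None of these is a bound, and the documents do not support saying that the reported figure will look far better than the relevant one. What they do show is that nothing in the plan keeps the gap small or makes it visible. This is an inexpensive improvement to the reporting; the pooled analysis itself is not invalid.

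**What to change.** In section 10.3.2, and correspondingly in the SAP:

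1. State one unit of analysis for an event, and the rule that links staff notes and diary entries to that unit.
2. Keep the complete-data specificity and label it as the overall false-alarm measure.
3. Report beside it, with intervals, specificity among monitored periods with recorded use (staff note or diary) and no overdose event, and specificity among periods with no recorded use. Give the number of units in each.
4. Base any conclusion about separating SIRD from non-overdose use on the recorded-use figure, not on the pooled one.
5. State as a limitation that use is under-recorded, because the diary is optional and staff note only observed evidence, so some use periods will sit in the group with no recorded use.

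**Cost.** No new data, visits or participants are needed. The work is a few sentences of text plus the linking rule, which the protocol now lacks. The recorded-use figure will have a smaller denominator, hence a wider interval, and will probably be less favourable.

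### Sensitivity and specificity are the only accuracy measures fixed for the alarm algorithm, with no unit for a true negative, so the primary analysis need not show how many alarms are false

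*Protocol*

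**What the plan says.** Protocol section 10.3.2 builds the primary analysis in four steps.

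- The index test is a retrospective alarm, yes or no: "Biosensor data analysed to determine whether or not an alarm would have been raised (and possibly the timing of the alarm").
- The reference is a staff judgement: "Staff measured outcomes reviewed to categorise whether there was cause for concern about the participant".
- The two are cross-classified: "Above measures compared to determine either True Positive / False Positive / True Negative / True Positive events". One category is printed twice and false negatives are missing. This is presumably a slip, since sensitivity cannot be computed without them.
- The summary is fixed: "Sensitivity and Specificity are calculated for the complete data set", ideally with some measure of error.

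No predictive value, alarm count or false-alarm rate is named there or elsewhere, and section 10.5 is marked not applicable. No unit is given for a negative. Section 10.4 excludes biosensor data that cannot be reconciled with staff and participant reports. Section 10.3 promises a statistical analysis plan before data lock.

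On purpose, section 2 (Rationale) says that such a sensor "could alert the emergency services and save lives, when fully developed and used in the community". It also says that the data should help to "accurately detect SIRD and differentiate from patterns that occur following substance use but do not result in an overdose".

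**The concern.** The algorithm is being developed for an alert. For an alert, the working questions are what share of alarms is real and how many false alarms a monitored resident generates. The Rationale's aim of separating overdose from other patterns after drug use is itself a question about false alarms.

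Sensitivity and specificity do not answer the first question without the event rate. Specificity does not answer the second unless the unit is known. Uneventful time dominates continuous recordings, so cutting it into shorter windows raises specificity with no change in the alarms. At stake is how the primary result is read: a high pair of percentages could be taken as evidence of a workable alert although most alarms were false.

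**Working it through.** The protocol states no event rate, accuracy target or sample size calculation (section 10.1), so there is no figure of its own to reproduce. Sensitivity (Se), specificity (Sp) and the proportion p of nights with staff-recorded concern are assumptions, shown over a range.

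**Inputs from the protocol.** About 50 participants (section 10.2). Each is observed for one night up to 4 weeks, extendable (study summary). Before extensions this is 50 × 1 = 50 to 50 × 28 = 1,400 nights.

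**Share of alarms that are real.** PPV = Se·p / [Se·p + (1 − Sp)(1 − p)]. With Se = 90%, in per cent:

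| Event nights, p | Sp 90% | Sp 95% | Sp 99% |
|---|---|---|---|
| 0.5% | 4.3 | 8.3 | 31.1 |
| 1% | 8.3 | 15.4 | 47.6 |
| 2% | 15.5 | 26.9 | 64.7 |
| 5% | 32.1 | 48.6 | 82.6 |
| 10% | 50.0 | 66.7 | 90.9 |
| 20% | 69.2 | 81.8 | 95.7 |

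The middle column at 1% is 0.9 × 0.01 / (0.9 × 0.01 + 0.05 × 0.99) = 0.0090 / 0.0585 = 15.4%.

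**Break-even.** PPV is 50% at p = (1 − Sp) / (Se + 1 − Sp). At 90/95 this is 0.05 / 0.95 = 5.3%. It is 10% at 90/90 and 1.1% at 90/99. Below these rates most alarms are false.

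**In counts.** At 1,400 nights and p = 1% there are 14 event nights. True alarms: 0.9 × 14 = 12.6. False alarms: 0.05 × 1,386 = 69.3. Then 69.3 / 81.9 = 85% of alarms are false, at 69.3 / 1,400 = about 5 per 100 nights. PPV does not depend on the number of nights.

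**Effect of the undefined unit.** Hold 14 events, 13 true alarms and 70 false alarms fixed over 1,400 nights, and assume 10 monitored hours per night. PPV is 13 / 83 = 15.7% throughout. Specificity is 1 − 70 / (number of units − 14):

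- per night: 1 − 70 / 1,386 = 94.9%
- per hour: 1 − 70 / 13,986 = 99.5%
- per 5 minutes: 1 − 70 / 167,986 = 99.96%

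The false-alarm rate stays at 70 / 1,400 = 5 per 100 nights.

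**Effect of section 10.4, if applied to disagreements.** The same night-level counts are 13 true positives, 1 false negative, 70 false positives and 1,316 true negatives. Removing the 71 discordant nights gives sensitivity 13/13, specificity 1,316/1,316 and PPV 13/13, all 100%. Adding PPV alone would then hide the problem.

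**The case against.** Sensitivity and specificity are standard measures for comparing a test with a reference, and section 10.3.2 does not forbid others. False positives are already a named category, so PPV and false-alarm counts can be derived from planned data, and the statistical analysis plan may add them. This is a feasibility study in which participants are told that the device will not issue an alert (section 2.1), and no accuracy threshold is set. All of this stands and limits the weight of the point. It does not remove it: the protocol specifies the primary measures by name and leaves their unit open, so nothing commits the report to showing alarm burden.

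The assumed event rates may also be too low. The reference is staff concern, which is broader than overdose, and every participant reports current opiate use (section 6.1). At 90/95 and 10% of nights, two thirds of alarms are real. This stands too, and is a reason to measure the quantity.

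Two further limits apply. An episode that staff missed would count as a false alarm, so PPV here means agreement with staff records. And once the night is the unit, the false-alarm rate is close to one minus specificity. Its value is that it keeps its meaning whatever window the algorithm uses.

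A reader might infer that the alarms will be mostly false, or that participants are at risk. The documents support neither: no event rate or algorithm performance is given, and staff welfare checks continue as usual. Nor does section 10.4 say outright that discordant classifications are dropped; that is one reading of it.

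**Conclusion.** The point holds as a weakness in the choice of primary measures. The fixed pair, with no unit for a true negative, cannot show alarm burden for an algorithm meant to drive an alert. Its size depends on an unknown event rate. At an assumed 90/95, the real share of alarms is about 15% at 1% of nights, about 49% at 5% and about 67% at 10%, with the break-even near 5%. For fixed alarms, specificity can range from 94.9% to 99.96% by choice of window alone, assuming 10 monitored hours per night. The consequence is a possible misreading of the result. It is not an error in the two measures themselves and not a safety problem in this study.

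**What to change.** In section 10.3.2:

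- Define the unit of analysis, for example the worn participant-night, and say whether repeated alarms within a unit count once.
- List all four categories, including false negatives.
- Report, alongside sensitivity and specificity, the positive predictive value and the false alarms per 100 worn participant-nights. Give intervals that allow for clustering of nights within participants.
- State that all of these are computed with sensor-staff disagreements kept as false positives or false negatives, and reword section 10.4 so that its exclusion does not reach them.

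A split by short term and long term residents is optional and descriptive only. At 1% of nights, even 1,400 nights yield 14 events, and 50 participants at an assumed 14 nights each (700 nights) yield 7, too few to divide usefully.

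The cost is small: the counts are already to be produced, and worn time comes from the recordings. The downside is a little more analysis and a headline that may look less favourable.
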